#### 6.13 Adverse Events Assessments

AEs will be recorded and reported in accordance with ICH Good Clinical Practice (GCP). The definitions of AEs and SAEs will be as given in the ICH Topic E2A, ICH Guideline "Note for Guidance on Clinical Safety Data Management: Definitions and Standards for Expedited Reporting."

## 6.13.1 Adverse Event Reporting

Patients will be instructed that they may report AEs at any time. AEs will be regarded as 'pre-treatment' if they occur between Screening and the time of administration of the first dose of APD811. All events reported following study medication administration will be recorded as treatment emergent AEs (TEAE).

Monitoring of AEs will be continued **up to 30 days** after study medication administration. In the event that an AE is not resolved or stabilized by this time, the sponsor in consultation with the investigator will decide whether to continue to monitor the AE or close-out the event in the database if no further follow-up is necessary.

For this study, an AE is defined as: "Any untoward medical occurrence in a study patient administered any dose of study medication (APD811 or placebo) and which does not necessarily have to have a causal relationship with this treatment." An AE can therefore be any unfavorable and unintended sign (including an abnormal laboratory finding), symptom, or disease temporally associated with the use of the study medication, whether or not related to the product. Worsening of underlying disease (section 6.9) will not be considered to be an adverse event.

AEs can be any of the following:

- Unfavorable changes in general condition
- Subjective or objective signs/symptoms
- Concomitant disease or accidents
- Clinically relevant adverse changes in laboratory parameters observed in a patient in the course of a clinical study

 Pre-existing conditions which worsen in severity or frequency or which have new signs/symptoms associated with them

Adverse events will be elicited at the time indicated in the schedule by asking the question: "Since you were last asked, have you felt unwell or different from usual in any way?" Any adverse or unexpected events, signs and symptoms, will be fully recorded on the Adverse Event Form including details of intensity, onset, duration, outcome and relationship to the drug as determined by the PI. Whenever possible, a constellation of signs and symptoms should be recorded as a unifying diagnosis (e.g., self-limited fever, runny nose, cough, and scratchy throat should be captured as an upper respiratory infection rather than by the individual signs and symptoms). AEs may also be reported at any time. The type and duration of follow-up of patients after AEs will be documented.

# 6.13.2 Serious Adverse Events and Expedited Reporting of Adverse Events

A Serious Adverse Event (SAE) is any untoward medical occurrence that at any dose results in the following outcomes:

- Death
- Is Life-Threatening
- Required/Prolonged Hospitalization
- Disability/Incapacity
- Congenital Anomaly/Birth Defect
- Important Medical Event

SAEs will be captured from the time of screening to 30 days after the dose of study drug, and will be monitored until resolution or stabilization.

An important medical event that may not result in death, be life-threatening, or require hospitalization may be considered a SAE when, based upon appropriate medical judgment, it may jeopardize the patient and may require medical or surgical intervention to prevent one of the outcomes listed in this definition. Examples of such a medical event includes allergic bronchospasm requiring intensive treatment in an emergency room or at home, blood dyscrasias, or convulsions that do not result in in-patient hospitalization, or the development of drug dependency or drug abuse.

Elective hospitalization and/or surgery for clearly pre-existing conditions (for example a surgery that has been scheduled prior to the patient's entry into the study) will not be reported as a SAE. All other hospitalizations, including elective hospitalizations for any condition that was not pre-existing, will be reported as a SAE.

All SAEs, whether or not considered related to study treatment, must be reported to the sponsor Contact within 24 hours of becoming aware of the event. In addition, a completed report using the sponsor's SAE form must be submitted within 24 hours of notification to:

Arena Drug Safety and Pharmacovigilance Arena Pharmaceuticals, Inc. [name]

Other situations as defined in ICH Topic E2A, 21 CFR§ 312.32, and EU Volume 10 also qualify for expedited reporting. In these situations the process will be as detailed for SAEs above:

- Serious adverse events which could be associated with the trial procedures;
- Serious adverse events and adverse events of special interest that could materially influence the benefit-risk assessment of a medicinal product, such as: a clinically important increase in the rate of a serious suspected adverse reaction over that listed in the investigator brochure.

Patients who become pregnant during the study will be discontinued immediately. Although not considered a SAE or AE, pregnancies occurring during the period of study drug administration (Day 1 of the dose titration period to Week 25/ Follow-up) until 30 days after the last dose of study drug should be reported to the sponsor Contact and IRB/IEC in the same manner as a SAE.

Pregnancies will be followed every trimester through the first well baby visit. For female partners who become pregnant by male study patients during the course of the study, reasonable efforts will be made to collect information on the partner's pregnancy through the first well baby visit as provided by the male study patient.

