#### 5.6.1 Dose Titration Period (up to 9 Weeks)

There will be a total of approximately 60 patients randomized to either active treatment or placebo in a 2:1 ratio. The starting dose is 0.01 mg APD811 twice daily (b.i.d.) or placebo. Thus, the identity of study drug (active or placebo) will be blinded, but the dose level is not. Patients will be observed for at least 4 hours after the initial dose of APD811 and after each subsequent dose escalation. A pre-dose and a 4-hour post-dose PK sample will be collected at each study visit in which dose escalation is planned. Adverse events, blood pressure, and heart rate will be monitored during the observation period. The observation period may be extended based on the judgment of the investigator. If deemed necessary by the investigator, the patient may be monitored as an in-patient for the initial dose and/or subsequent increases in dose. The medical monitor should be notified in any instance that prolonged observation and/or in-patient monitoring is anticipated or required.

If a dose is not tolerated, the study drug may be decreased to the previous dose level. If the initial dose of 0.01 mg b.i.d. is not tolerated, dosing may be decreased to 0.01 mg q.d.

If the initial dose is tolerated (0.01 mg b.i.d.), the dose will be increased in the following fashion at subsequent visits: 0.02 mg b.i.d., 0.03 mg b.i.d., 0.04 mg b.i.d., 0.06 mg b.i.d., 0.08 mg b.i.d., 0.1 mg b.i.d., 0.2 mg b.i.d and 0.3 mg b.i.d. The dose may be escalated to a maximum total daily dose of 0.6 mg (0.3 mg b.i.d.) depending on tolerability.

Prolonged dosing may result in tolerance to some adverse effects and thus, more than 1 week between dose escalations may be required. However, Investigators are encouraged to dose escalate to the highest possible dose within the 9-week dose titration period. If a particular dose is not tolerated, treatment may be reduced to a previous dose as directed by the investigator. The dose may be decreased for safety reasons at any time, but may not be increased without assessment in the clinic.

Table 3 indicates the dosing regimen during the 9-week dose titration period. This dosing regimen (starting dose, dose increments, dosage forms, duration) may be modified during the course of the study by the Safety Monitoring Committee based on cumulative patient experience. In order to simplify dose titration, the 0.01 mg dose strength will be used during the initial portion of the dose titration.

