# 6.15 Removal of Patients from the Trial or Study Drug

The study will be terminated early if, in the opinion of the sponsor, investigator, or IRB/IEC, an unacceptable risk to the safety and welfare of patients is posed by the continuation of the study in light of review of the key safety data.

Patients will be informed that they are free to withdraw from the study at any time for any reason should they so wish. The PI may remove a patient if, in his/her opinion, it is in the best interest of the patient. A patient may be withdrawn from the study for any of the following reasons:

- Clinical worsening as defined in Section 6.9
- Deviation/noncompliance with the protocol,
- A serious or intolerable AE occurs,
- The sponsor or investigator terminates the study, or
- Withdrawal of consent any patient may withdraw his/her consent from the study at any time. The investigator should make a reasonable attempt to document the specific reason why consent is withdrawn.

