5.3 Adverse Events

Adverse events will be coded using the most current Medical Dictionary for Drug Regulatory Affairs (MedDRA) and tabulated, including categorical information of interest such as onset and resolution times, time of onset relative to dose, severity at onset, maximum severity, causal

relationship to study medication, and action taken. AEs will be regarded as ‘pre-treatment’ if they occur between screening and the time of administration of the first dose of APD811 or placebo and will be recorded as medical history. All other AEs that occur or worsen after the first dose of study medication will be considered to be ‘treatment-emergent’. Missing or incomplete start date of AE will be imputed as section 7.4.

Treatment-emergent AEs (TEAE) will be listed by patient and by treatment. They will be summarized per treatment and expressed in terms of maximum severity and relationship to study medication. The incidence of TEAEs classified according to system organ class will be summarized by treatment group. TEAEs will also be summarized by maximum intensity (assessed according to the Common Terminology Criteria for Adverse Events v4.03² definitions) and relatedness to study medication.

Summaries of the number (%) of patients in each treatment group with at least 1 TEAE, classified according to MedDRA system organ class and preferred term, will also be provided for:

- Drug-related TEAE
- Treatment-emergent AEs leading to permanent discontinuation of study medication (study medication discontinued or withdrawal from study).
- Serious adverse events (SAEs)
- Prevalence of selected treatment-emergent AEs over dose titration and treatment periods

Serious adverse events will be listed by patient and by treatment. If there are no SAEs at the end of the study, the tables or listings will state that there are no SAEs in the study.

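### Protocol 6.13.2 defines an SAE as an untoward event, then tells sites to report all but one kind of hospitalization as an SAE, so event-free observation stays permitted by 5.6.1 may be reported differently from site to site

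*Protocol*

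**What the plan says.** Protocol 6.13.2 opens with a definition: "A Serious Adverse Event (SAE) is any untoward medical occurrence that at any dose results in the following outcomes". Required or prolonged hospitalization is one of the outcomes listed. The introduction to 6.13 takes the AE and SAE definitions from ICH E2A.

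Later in 6.13.2 there is a separate paragraph on hospitalization. It removes one class from SAE reporting, "Elective hospitalization and/or surgery for clearly pre-existing conditions", with the example of an operation already booked before the patient joined the study. It then continues: "All other hospitalizations, including elective hospitalizations for any condition that was not pre-existing, will be reported as a SAE".

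Protocol 5.6.1, on dose titration, provides for observation in hospital: "If deemed necessary by the investigator, the patient may be monitored as an in-patient for the initial dose and/or subsequent increases in dose". The only step attached to such a stay is to notify the medical monitor, and that step also covers stays foreseen in advance.

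SAP 5.3 lists SAEs by patient and treatment. It also includes SAEs among its summaries of the number and percentage of patients per group with treatment-emergent events.

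**The concern.** The definition and the hospitalization rule use different tests. The definition asks whether something untoward happened. The rule asks only whether the patient was hospitalized and whether the single exemption applies. For most admissions the two agree. They part company for a stay arranged only to watch the patient after a dose step, which is the kind of stay 5.6.1 permits.

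Two sites could follow the same section in good faith and classify the same stay differently. What is at stake is the meaning of the SAE count. Safety and tolerability is a secondary objective in Protocol 2.2 (the SAP lists it as a separate safety objective). With small arms, a few stays of this kind would be visible in the SAE percentages. Each one reported also starts the 24-hour process in 6.13.2.

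**Working it through.** The plan states no figure on this point, so the check is mainly a comparison of text.

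**1. Apply each provision to one case: a planned in-patient stay at a dose increase, with no adverse event before or during it.**

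- *Definition (6.13.2 lead-in, with ICH E2A through 6.13).* An untoward occurrence is needed and there is none. Result: not an SAE.
- *Exemption (6.13.2).* This needs an elective admission for a clearly pre-existing condition. The purpose of the stay is to observe the response to study drug, although a site could argue that it is elective care for pre-existing PAH. Result: unclear.
- *Catch-all (6.13.2).* If the exemption does not apply, the stay is one of the remaining hospitalizations, and the sentence has no further condition. Result: report as an SAE.

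The same stay therefore receives two answers within one section.

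**2. Look for text that settles it.** Nothing in Protocol 5.6.1, in the AE and SAE text of 6.13, or in SAP 5 to 5.3 exempts these stays or says how to record them.

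**3. Follow a stay that a site does report.** It goes to the sponsor within 24 hours (6.13.2). Protocol 6.13.1 treats events reported after study medication has been given as treatment-emergent, so a stay reported after a dose increase could appear in the SAP 5.3 listing and, once coded, in the SAE summary. SAP 5.3 has no filter for it.

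**4. Scale.**

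- Occasions on which a stay is permitted, from the schedule in 5.6.1: 1 first dose + 8 increases = 9 per patient. An incidence table counts a patient once, so 9 is the number of opportunities and not a multiplier.
- Arm sizes, from Protocol 9.3: 40 APD811 and 20 placebo, taking all randomized patients as dosed.
- If k patients in an arm of size n have an observation stay as their only reported SAE, incidence rises by 100 × k / n percentage points.
- For k = 1: 100 × 1/40 = 2.5 points on APD811, and 100 × 1/20 = 5.0 points on placebo.
- The documents do not give the expected k. Over an assumed range of 0 to 4 patients in an arm, the rise is 0 to 10 points on APD811 (100 × 4/40 = 10) and 0 to 20 points on placebo (100 × 4/20 = 20).

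**The case against.** The strongest reply is that the definition governs. The hospitalization paragraph sits beneath it and can be read as explaining the hospitalization outcome, so an event-free stay is not an AE and cannot be an SAE. This reading is reasonable. It rules out the claim that every such stay has to be reported. It does not remove the conflict, because the later sentence is a specific, mandatory instruction with no such limit.

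A second reply is that all patients have pre-existing PAH, so a planned titration stay falls within the exemption. That is arguable, but the exemption's own example is surgery arranged before study entry, which is a different situation. The argument adds a third way for a site to decide.

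A third reply is that an event-free stay has nothing to code, grade or attribute, and so may never become a row in a table of treatment-emergent events. This stands in part: entry into the SAE summary is possible, not certain. The by-patient listing would also let a reader identify such stays, provided the entry says why the patient was admitted.

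A reader might draw three stronger conclusions, and the documents do not support them:

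- *That the extra SAEs would fall mainly on APD811.* Section 5.6.1 leaves the dose level unblinded in both arms, and no admission rates are given. A patient admitted because an earlier step went badly has already had an adverse event, and that admission may be a genuine SAE. Any numerical contrast between arms would only return the rates assumed for it.
- *That overnight stays for right heart catheterization are caught too.* Neither document mentions an overnight stay for that procedure.
- *That a misreported stay leads to withdrawal.* Protocol 6.15 does list "A serious or intolerable AE occurs" as a reason, but withdrawal there is discretionary and an adverse event is needed.

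**Conclusion.** The concern holds as an internal conflict in Protocol 6.13.2. For an event-free observation stay under 5.6.1, the definition gives one answer and the reporting sentence gives another, and nothing in either document decides between them. Sites may report differently, and SAE listings and counts by arm may include stays with no untoward event.

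The effect is confined to SAE counts and expedited reporting; the PVR and 6MWD analyses are untouched. Per patient misclassified, the shift is 2.5 points on APD811 or 5 points on placebo. This assumes that all 40 and 20 randomized patients are dosed and that the patient has no other SAE. How many such stays to expect, and whether they would differ by arm, cannot be determined from the documents. The correction is worth making because it is cheap beforehand, whereas afterwards the reported stays would have to be reviewed one by one.

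**What to change.** Reconcile the two sentences in Protocol 6.13.2 by adding text to this effect: admission solely for the observation permitted in Section 5.6.1, with no adverse event, is not in itself an SAE; any adverse event that causes the stay, occurs during it or prolongs it is assessed against the usual SAE criteria. Carry the same wording into the SAE reporting instructions.

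Record observation stays on one CRF item, and have the SAP report their number by arm beside the SAE table. The stays then remain visible without being counted as SAEs.

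The cost is a short addition to the protocol and SAE instructions, one CRF item and one line of SAP output. No dosing or monitoring rule changes.

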## 6.13.3 Assessment of Adverse Event Severity

The severity of each AE will be assessed at onset by a nurse and/or physician. When recording the outcome of the AE the maximum severity of the AE experienced will also be recorded. The severity of the AE will be graded according to the CTCAE v4.03 definitions, listed below:

- **Grade 1:** Mild; asymptomatic or mild symptoms; clinical or diagnostic observations only; intervention not indicated.
- **Grade 2:** Moderate; minimal, local or noninvasive intervention indicated; limiting age-appropriate instrumental Activities of Daily Living (ADL)\*.
- **Grade 3:** Severe or medically significant but not immediately life-threatening; hospitalization or prolongation of hospitalization indicated; disabling; limiting self-care ADL\*\*.
- **Grade 4:** Life-threatening consequences; urgent intervention indicated.
- **Grade 5:** Death related to AE.

#### **Activities of Daily Living (ADL)**

\*Instrumental ADL refer to preparing meals, shopping for groceries or clothes, using the telephone, managing money, etc.

\*\*Self-care ADL refer to bathing, dressing and undressing, feeding self, using the toilet, taking medications, and not bedridden.

## 6.13.4 Assessment of Adverse Event Relationship to Study Medication

The relationship of an AE to investigational product(s) will be classified using modified WHO criteria (Edwards and Biriell, World Health Organization Collaborating Centre for International Drug Monitoring 1994) as follows.

**Related**: a clinical event, including laboratory test abnormality, with a reasonable time sequence to administration of the drug, unlikely to be attributed to concurrent disease or other drugs or chemicals, and which follows a clinically reasonable response on withdrawal (dechallenge). Rechallenge information is not required to fulfill this definition; or an event that could also be explained by concurrent disease or other drugs or chemicals where information on drug withdrawal may be lacking or unclear.

**Not related**: a clinical event, including laboratory test abnormality, with sufficient evidence to accept that there is no causal relationship to drug administration (e.g., no temporal relationship to drug administration, because the drug was administered after onset of event; investigation shows that the drug was not administered; proof of other cause; etc.); or an event with a temporal relationship to drug administration which makes a causal relationship improbable, and in which other drugs, chemicals or underlying disease provide plausible explanations.

#### 6.13.5 Assessment of Adverse Event Outcome

Outcome of AEs will be defined according to ICH Topic E2B, ICH Guideline.

- Recovered/Resolved
- Recovering/Resolving
- Not Recovered/Not Resolved
- Recovered/Resolved with Sequelae
- Fatal
- Unknown

#### 6.13.6 Action Taken for Adverse Event

Action taken for AEs will be documented according to the following:

- Concomitant medication or other treatment
- Withdrawal from the study

#### 6.13.6.1 Action Taken for Study Drug

Any action taken with study drug will be defined according to ICH Topic E2B, ICH Guideline and documented in the CRF according to the following:

- Drug Withdrawn
- Dose Reduced
- Dose Increased
- None (not changed)
- Dose Interrupted
- Unknown
- Not Applicable

## 6.13.7 Collection of Extra Laboratory Samples/Investigations

In the event of a clinically important AE, a suitable blood sample may be collected for additional laboratory tests. The investigator must ensure that the sample is properly labeled and stored. The investigator and others responsible for care of the patients should institute any supplementary investigations of significant AEs based on the clinical judgment of the likely causative factor. This may include seeking a further opinion from a specialist in the field of the AE. The company may suggest special tests based on expert advice.

## 6.13.8 Follow-up of Adverse Events Present at Last Scheduled Study Visit

Adverse events present at the last study day (Week 25/Follow-up) that require follow-up or a repeat laboratory test will be followed-up initially for 30 days according to the CRO's procedures for AE follow-up. AEs that have not resolved or stabilized at 30 days after the last patient's last study dose, will be reviewed with the sponsor on an individual basis to determine whether the database will be locked and subsequently updated once the events of ongoing AEs are resolved or whether database lock will be held.

#### 6.14 Concomitant Medication Assessments

All concomitant medications (OTC and prescribed) taken by patients during the screening period and during the study will be recorded in the CRF with indication, start date/time and stop date/time, if known.

Patients will be permitted oral disease-specific PAH therapy consisting of an endothelin receptor antagonist (ERA) and/or an agent acting on the nitric oxide pathway, PDE5 inhibitor or a soluble guanlyate cyclase stimulator at a stable dose for at least **3 months** prior to the start of Screening, and should continue the same dose and regimen of these medications for the duration of the study.

The use of the following therapies, which may affect PAH, are permitted if on a stable dose for at least 1 month prior to Screening and should remain unchanged during the study:

- vasodilators (including calcium channel blockers)
- digoxin
- spironolactone
- L-Arginine supplementation

Previous administration of a prostacyclin or prostacyclin analogue is not permitted if treatment was stopped for a safety or tolerability issue. In addition, intravenous inotropes within **1 month** of Screening are not permitted.

Diuretics may be dosed as clinically indicated throughout the study.

Additionally, the use of PDE-5i as needed for erectile dysfunction (ED) is permitted as long as the patient has not taken a dose within **48-hours** of any Baseline or study related efficacy assessment. In addition, the patient must not take more than 8 sildenafil tablets, 6 vardenafil, or 4 tadalafil tablets **per month** for ED.

